N	Number (typically refers to subjects)
NIH	National Institutes of Health
OP	Oropharyngeal
PBO	Placebo
PCR	Polymerase Chain Reaction
PI	Principal Investigator
PO	"Per os", by mouth
PT	Preferred Term / Prothrombin Time

RCD	Reverse Cumulative Distribution
RDV	Remdesivir
RMST	Restricted Mean Survival Time
RNA	Ribonucleic Acid
SAE	Serious Adverse Event
SAP	Statistical Analysis Plan
SARS	Severe Acute Respiratory Syndrome
SD	Standard Deviation
SDCC	Statistical and Data Coordinating Center
SOC	System Organ Class
SQ	Subcutaneous
US	United States
WBC	White Blood Cell
WHO	World Health Organization

1. PREFACE

The Statistical Analysis Plan (SAP) for “A Multicenter, Adaptive, Randomized Blinded Controlled Trial of the Safety and Efficacy of Investigational Therapeutics for the Treatment of COVID-19 in Hospitalized Adults” (DMID Protocol 20-0006) describes and expands upon the statistical information presented in the protocol. This protocol is an adaptive protocol with different stages. Each stage will have a separate SAP. This SAP is for the study’s 4th stage “ACTT-4”: Baricitinib + Placebo + Remdesivir vs. Placebo + Dexamethasone + Remdesivir.

This document describes all planned analyses and provides reasons and justifications for these analyses. It also includes sample tables, listings, and figures planned for the final analyses. Regarding the final analyses and Clinical Study Report (CSR), this SAP follows the International Conference on Harmonisation of Technical Requirements for Registration of Pharmaceuticals for Human Use (ICH) Guidelines, as indicated in Topic E3 (Structure and Content of Clinical Study Reports), and more generally is consistent with Topic E8 (General Considerations for Clinical Trials) and Topic E9 (Statistical Principles for Clinical Trials). The structure and content of the SAP provides sufficient detail to meet the requirements identified by the Food and Drug Administration (FDA) and ICH, while all work planned and reported for this SAP will follow internationally accepted guidelines published by the American Statistical Association and the Royal Statistical Society for statistical practice.

This document contains: a review of the study design, general statistical considerations, comprehensive statistical analysis methods for efficacy and safety outcomes, and a list of proposed tables, figures and listings. Within the table, figure, and listing mock-ups ([Appendix 1](#), [Appendix 2](#), [Appendix 3](#)), references to CSR sections are included. Any deviation from this SAP will be described and justified in protocol amendments and/or in the CSR, as appropriate. The reader of this SAP is encouraged to also review the study protocol for details on conduct of the study and the operational aspects of clinical assessments.

2. INTRODUCTION

Data from ACTT-1 showed that hospitalized adults with COVID-19 who were randomized to receive remdesivir alone resulting in the U.S. Food and Drug Administration (FDA) issuing an Emergency Use Authorization (EUA) to permit the use of remdesivir for treatment of suspected or laboratory-confirmed COVID-19 in adults and children hospitalized with severe disease. Remdesivir has also received, full or conditional approval in several other countries. On August 28, 2020, the FDA expanded the scope of the EUA to include hospitalized patients with suspected or laboratory-confirmed mild or moderate COVID-19 based on final data from ACTT-1 and two other clinical studies.

While remdesivir is considered the standard antiviral for COVID-19, significant morbidity and mortality still occur despite its use. Early in the outbreak, it was observed that COVID-19 patients who developed severe respiratory disease including acute respiratory distress syndrome (ARDS) had increased levels of cytokines consistent with that seen in patients infected with other pathogenic coronaviruses (e.g., SARS). It is postulated that this dysregulated inflammatory immune response contributes to the excessive mortality and targeting this response would further improve outcomes. While multiple strategies have been proposed to counter the hyper-inflammation, to date only two anti-inflammatory strategies have demonstrated efficacy in large randomized trials – dexamethasone and baricitinib.

In ACTT-2, subjects receiving the combination treatment of baricitinib and remdesivir had a shorter median time-to-recovery of 7 days (95% confidence interval (CI), 6 to 8 days) when compared with patients who received remdesivir and placebo (8 days; 95% CI, 7 to 9 days) with control [rate ratio for recovery [RRR] 1.16, 95% CI 1.01 to 1.32; P=0.03]. Patients who received combination treatment were 30% more likely to have clinical improvement by day 15 than those in the control arm (odds ratio [OR] 1.3; 95%CI 1.0 to 1.6). The patients who benefited the most from combination treatment were those requiring high-flow oxygen or non-invasive ventilation at enrollment with a median of 10 days to recovery compared with 18 days in control group (RRR 1.5, 95% CI 1.1 to 2.1) and the best clinical improvement by day 15 (OR 2.2; 95% CI 1.4 to 3.6). Baricitinib also showed benefit to those on low flow oxygen with a median of 5 days to recovery compared with 6 days in control group (RRR 1.17, 95% CI 0.98 to 1.39) and the clinical improvement by day 15 (OR 1.2; 95% CI 0.9 to 1.6). Patients who received combination treatment with baricitinib and remdesivir and those in the control arm had a similar incidence of adverse and serious adverse events including infections and venous thromboembolic events (VTE).

The Randomized Evaluation of COVID-19 Therapy (RECOVERY) trial is a controlled, open-label randomized trial, involving all major hospitals in the UK. The trial compared a range of possible treatments in patients who were hospitalized with COVID-19. Included, was a treatment arm assigned to receive oral or intravenous dexamethasone (at a dose of 6 mg once daily for up to 10 days) or to received usual care alone. Overall, 22.9% in the dexamethasone group and 25.7% in the usual care group died within 28 days after randomization (age-adjusted rate ratio, 0.83; 95% confidence interval [CI], 0.75 to 0.93; P<0.001). In the dexamethasone group, the incidence of death was lower than that in the usual care group among patients receiving invasive mechanical ventilation (29.3% vs. 41.4%; rate ratio, 0.64; 95% CI, 0.51 to 0.81) and among those receiving supplemental oxygen without invasive mechanical ventilation (23.3% vs. 26.2%; rate ratio, 0.82; 95% CI, 0.72 to 0.94) but not among those who were receiving no supplemental oxygen respiratory support at randomization (17.8% vs. 14.0%; rate ratio, 1.19; 95% CI, 0.91 to 1.55). Remdesivir was not used routinely in the RECOVERY trial.

The ACTT-2 and RECOVERY trials are very different and direct comparison is difficult (see Protocol Appendix D Section 2.2.1) However, the relative risk ratios also suggest these two anti-inflammatory strategies may be optimal in different inpatient populations, with baricitinib having the larger effect in the

high flow or low flow oxygen group and dexamethasone having the largest effect in those on mechanical ventilation.

For this reason, direct comparison of these two anti-inflammatory interventions is important. ACTT-4 will evaluate patients hospitalized with COVID-19 and requiring oxygen and determine if baricitinib or dexamethasone (both in addition to remdesivir) is superior or if they are comparable.

2.1. Purpose of the Analyses

This SAP encompasses all interim analyses and the final analysis of primary and secondary outcome measures. These analyses will assess the efficacy and safety of baricitinib + remdesivir in comparison with dexamethasone + remdesivir and will be included in the Clinical Study Report. This protocol is an adaptive design and, if the design is modified, the SAP will be amended accordingly. Safety interim analyses will occur on an ongoing basis to review safety data in the event that the experimental agents inflicts harm. A single interim efficacy analysis will be conducted if enrollment of 1/3 of all subjects is not completed within 1.5 months of study activation. More rapid enrollment will obviate the interim analysis since only a small fraction of remaining enrollment would be impacted by resulting decisions. The goal of the efficacy interim analyses is to review endpoint data in order to recommend whether the current study arm should proceed or to stop early for benefit or futility.

This SAP describes the planned analysis to be conducted by the Investigational New Drug (IND) sponsor NIAID. The analyses in this SAP are intended to be executed to support a Clinical Study Report (CSR) following the last patient's Study Visit Day 60, including all primary and secondary endpoints. Protocol-defined exploratory analyses and additional analyses, if any, performed by the product manufacturer may be pre-specified and described in an addendum to this SAP.

3. STUDY OBJECTIVES AND ENDPOINTS

3.1. Study Objectives

Primary Objective

To evaluate the clinical efficacy of baricitinib + remdesivir versus dexamethasone + remdesivir as assessed by the **mechanical ventilation free survival** by Day 29.

Secondary Objectives

The key secondary objective is to evaluate the clinical efficacy of baricitinib + placebo + remdesivir versus placebo + dexamethasone + remdesivir according to the clinical status 8-point ordinal scale at Day 15.

The other secondary objectives are to evaluate clinical efficacy of baricitinib + placebo + remdesivir as compared placebo + dexamethasone + remdesivir as assessed by:

- Among subjects with actual baseline Clinical Status ordinal score in Ordinal Score 5, the proportion that do not progress to Clinical Status score 6, 7, or 8 at any time prior to Day 29.
- Mortality
 - Death by Day 15
 - Death by Day 29
- Time to recovery by Day 29.
- Time to an improvement of one category and two categories from Day 1 using the ordinal scale.
- Subject clinical status using 8-point ordinal scale at Days 3, 5, 8, 11, 15, 22, and 29.
- Desirability of Outcome Ranking (DOOR) at Day 15 and Day 29.
- Oxygenation:
 - Oxygenation use up to Day 29.
 - Incidence and duration of new oxygen use through Day 29.
- Non-invasive ventilation/high flow oxygen:
 - Non-invasive ventilation/high flow oxygen use up to Day 29.
 - Incidence and duration of new non-invasive ventilation or high flow oxygen use through Day 29.
- Invasive Mechanical Ventilation / extracorporeal membrane oxygenation (ECMO):
 - Ventilator/ECMO use up to Day 29.
 - Incidence and duration of new mechanical ventilation or ECMO use through Day 29.
- Duration of hospitalization (in days) through Day 29.
- Laboratory Efficacy assessed by d-dimer, and C-reactive protein (CRP) over time

Safety Objectives

Evaluate the safety of baricitinib + remdesivir and dexamethasone + remdesivir through 29 days of follow-up as assessed overall by:

- Cumulative incidence of SAEs through Day 29
- Cumulative incidence of Grade 3 and 4 clinical and/or laboratory AEs through Day 29.
- Discontinuation or temporary suspension of study product administrations (for any reason).
- Changes in white cell count (WBC) with differential, hemoglobin, platelets, creatinine, glucose, total bilirubin, alanine aminotransferase (ALT), aspartate aminotransferase (AST), prothrombin time (PT reported as and INR) over time (analysis of lab values in addition to AEs noted above).

Exploratory Objective

The exploratory objectives are:

1. Evaluate alternate Desirability of Outcome Ranking (DOOR) scales to combine safety and efficacy.
2. To evaluate the virologic efficacy of baricitinib + remdesivir as compared to dexamethasone + remdesivir as assessed by:
 - Percentage of subjects with SARS-CoV-2 detectable in oropharyngeal (OP) sample at Day 3, 5, 8, 11, 15, and 29.
 - Quantitative SARS-CoV-2 virus in OP sample at Day 3, 5, 8, 11, 15, and 29.
 - Quantitative SARS-CoV-2 virus in blood at Day 3, 5, 8, and 11.
3. To evaluate the influence of baricitinib and dexamethasone on SARS-CoV-2 antibody response.
4. To define immunophenotype of subjects by analyzing markers of inflammation, transcriptomics.
5. To describe clinical status of subjects 2 months after treatment, overall and by treatment arm.

3.2. Endpoints

The 8-point ordinal scale is utilized as the principal clinical assessment tool during the study and is the basis for the primary and multiple secondary endpoints. The 8-point ordinal scale is defined as (worst to best):

Category 8: Death;

Category 7: Hospitalized, on invasive mechanical ventilation or ECMO;

Category 6: Hospitalized, on non-invasive ventilation or high flow oxygen devices;

Category 5: Hospitalized, requiring supplemental oxygen;

Category 4: Hospitalized, not requiring supplemental oxygen - requiring ongoing medical care (COVID-19 related or otherwise);

Category 3: Hospitalized, not requiring supplemental oxygen - no longer requiring ongoing medical care. This would include those kept in hospital for quarantine/infection control, awaiting bed in rehabilitation facility or homecare, etc.;

Category 2: Not hospitalized, but has new or increased limitation on activities and/or new or increased requirement for home oxygen over baseline, pre-COVID-19 status;

Category 1: Not hospitalized, patient is back to their baseline, pre-COVID-19 status, that is, no new or increased limitations on activities and no new or increased oxygen use compared with baseline.

Primary Endpoint

Mechanical ventilation free survival by Day 29 will be assessed as the proportion of subjects not meeting criteria for either of the following categories on the 8-point ordinal scale at any time before or at Day 29.:

Category 8: Death

Category 7: Hospitalized, on invasive mechanical ventilation or ECMO

Secondary Endpoints

The key secondary endpoint is the proportion of subjects meeting criteria for each of the 8-point ordinal scale categories on Day 15.

Other Secondary Endpoints are:

- Proportion of subjects not meeting criteria for one of the following ordinal scale categories at any time by Day 29

Category 8: Death

Category 7: Hospitalized, on invasive mechanical ventilation or ECMO

Category 6: Hospitalized, on non-invasive ventilation or high flow oxygen devices

- Days from randomization and cause of death (if applicable).

- The time to recovery defined as the days from randomization to the first day on which the subject satisfies the criteria for any of the following three categories on the 8-point ordinal scale at any time before or at Day 29:

Category 3: Hospitalized, not requiring supplemental oxygen - no longer requiring ongoing medical care. This would include those kept in hospital for quarantine/infection control, awaiting bed in rehabilitation facility or homecare, etc.;

Category 2: Not hospitalized, but has new or increased limitation on activities and/or new or increased requirement for home oxygen over baseline, pre-COVID-19 status;

Category 1: Not hospitalized, patient is back to their baseline, pre-COVID-19 status, that is, no new or increased limitations on activities and no new or increased oxygen use compared with baseline.

- The time improvement of one category in score defined as the days from randomization to the first day on which the subject satisfies the criteria for a category at least one-step better (e.g., 5 to 4) than their baseline category.
- The time improvement of two categories in score defined as the days from randomization to the first day on which the subject satisfies the criteria for a category at least two-steps better (e.g., 5 to 3) than their baseline category.
- The proportion of subjects meeting the criteria for each of the 8-point ordinal scale categories while hospitalized (Days 3, 5, 8, 11) and on Days 15, 22 and 29.

- Proportion of subjects in each level of the Desirability of Outcome Ranking (DOOR) categories at Day 15 and Day 29. DOOR levels are based on the 8-point ordinal score and the occurrence or absence of SAEs prior to or on the date of the assessment, defined as (best to worst):
 - 1 - Recovered (Category 1, 2 or 3 Ordinal Score)
 - 2 - Improved (≥ 1 category improvement in Ordinal Score compared with baseline) & no SAE
 - 3 - Improved (≥ 1 category improvement in Ordinal Score compared with baseline) & SAE (related or unrelated)
 - 4 - No change in Ordinal Score from baseline & no SAE
 - 5 - No change in Ordinal Score from baseline & SAE (related or unrelated)
 - 6 - Worsening (≥ 1 category worse in Ordinal Score compared with baseline)
 - 7 - Death
- Days of supplemental oxygen (if applicable) up to Day 29.
- Days of non-invasive ventilation/high-flow oxygen (if applicable) up to Day 29.
- Days of invasive mechanical ventilation/ECMO (if applicable) up to Day 29.
- Days of hospitalization up to Day 29.
- D-dimer and CRP on Day 1, while hospitalized (Days 3, 5, 8, 11), and on Days 15 and 29 (if attends in-person visit or still hospitalized).

Safety Endpoints

Safety endpoints are:

- SAEs
- Grade 3 and 4 treatment emergent adverse events
- Incidence and number of discontinuation or temporary suspension of study product
- WBC with differentials, hemoglobin, platelets, creatinine, glucose, total bilirubin, ALT, AST, INR, on Day 1; Days 3, 5, 8, and 11 (while hospitalized); and Days 15 and 29 (if attends in-person visit or still hospitalized).

Exploratory Endpoints

- Alternate DOOR scales

None of the remaining exploratory endpoints will be described in this SAP, but they include the following:

- Virology endpoints:
 - Qualitative and quantitative polymerase chain reaction PCR for SARS-CoV-2 in OP swab on Day 1; Days 3, 5, 8, and 11 (while hospitalized); and Days 15 and 29 (if attends in-person visit or still hospitalized).
 - Qualitative and quantitative PCR for SARS-CoV-2 in blood on Day 1; Days 3, 5, 8, and 11 (while hospitalized).
- Serology endpoint: SARS-CoV-2 antibody titers on Day 1, 8, and 29.

- Immunophenotype endpoints:
 - Proteomic analysis of cytokines, markers of inflammation, and other circulating proteins on Day 1; Days 3, 5, 8, and 11 (while hospitalized) and Day 29.
 - Additionally, in a subset of subjects who consent to genetic testing, transcriptomic analysis of RNA in whole blood and individual immune cells on Days 1, 3, 8, and 29.
- Chronic Clinical Sequelae: Ordinal score, incidence of supplemental oxygen use and physical disability (more than baseline pre-COVID-19 status), readmission to hospital; proportion of subjects with new diagnoses including deep venous thrombosis (DVT), infections, post-traumatic stress disorder (PTSD), anxiety and/or depression.

3.3. Study Definitions and Derived Variables

3.3.1. Baseline Value

For efficacy assessments, the baseline value will be defined as the last value obtained prior to randomization. For safety assessments, the baseline value will be defined as the last value obtained prior to the first on-trial dose of any study product (baricitinib, dexamethasone, remdesivir, or placebo). If the exact time of the assessment or the first dose is not available, but collected on the same date, the assessment will be assumed to have occurred prior to receipt of study product.

A small subset of subjects may receive dexamethasone as standard of care on the same day as but prior to randomization then forgo the dexamethasone / placebo component of the Day 1 study product administration. For these subjects, the baseline value of efficacy assessments will be the last value prior to randomization, as in the preceding paragraph. But, for these subjects, the value of baseline safety assessments will be defined as the last value obtained prior to the dexamethasone dose. If the exact time of the assessment of the pre-randomization dexamethasone or on-trial doses of study product are not available, but collected on the same date, the assessments will be assumed to have occurred prior to receipt of study product and prior to randomization.

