4.2.1. Treatments Administered

Dosing of the medications does not need to occur at the same time. All subjects receive remdesivir as a 200 mg intravenous (IV) loading dose on Day 1, followed by a 100 mg once-daily IV maintenance dose for the duration of the hospitalization up to a 10-day total course. If subjects already received the loading dose prior to study enrollment, then start at 100 mg/day on Day 1. Any doses of remdesivir given prior to enrollment will be counted, so the total duration of remdesivir (i.e. pre-enrollment + on this trial) is 10 days (i.e., a maximum of 10 total infusions). Any doses of remdesivir were administered prior to study enrollment should be documented in Advantage eClinical as a concomitant medication given prior to Day 1. The duration of dosing may be adjusted by the site similar to what is described in the package insert and based on a subject's clinical course and ultimate disease severity.

For the baricitinib component, subjects receive either active product or placebo as follows:

- Baricitinib will be administered as a 4 mg orally (po) (two 2mg tablets) or dissolved for NG tube, daily for the duration of the hospitalization up to a 14-day total course.
- A placebo will be given as two tablets po or dissolved for NG tube, daily for the duration of the hospitalization up to a 14-day total course.
 - Any pre-study dexamethasone (max 1 dose per inclusion criteria) is not counted towards the 10-day course.

For dexamethasone component, subjects receive either active product or placebo as follows:

- Dexamethasone administered as a 6 mg slow IV push over 3 to 5 minutes daily for the duration of the hospitalization up to a 10-day total course.

- A placebo will be given as an equal volume normal saline, as a slow IV push daily for the duration of the hospitalization up to a 10-day total course.
- If site local standards use other means of administration (such as IV infusion), these may be used for both active and placebo after approval of the sponsor.
- Any pre-study dexamethasone (max 1 dose per inclusion criteria) is not counted towards the 10 day course.

Duration of therapy:

- IV remdesivir – up to 10 days while hospitalized (i.e., maximum of 10 total infusions pre-enrollment and during study).
- Oral baricitinib (or oral placebo) – 14 days while hospitalized (i.e., maximum of 14 total doses).
- IV dexamethasone (or IV placebo) – 10 days while hospitalized (i.e., maximum of 10 total doses).

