9.3. Adverse Events

For the calculation of incidence of adverse events (i.e., on a per subject basis), each subject will only be counted once and any repetitions of adverse events within a subject will be ignored; the denominator will be the number of subjects in the As Treated population. All adverse events reported and treatment emergent will be reported in tables and listings; treatment emergent events are adverse events or events increasing in severity anytime following the initiation of administration with any study product (baricitinib, dexamethasone, remdesivir, or any placebo).

An overall summary by treatment arm and actual baseline ordinal score of adverse events is presented that includes, but not limited to: subjects with at least one event, at least one related event, at least one SAE, at least one related SAE and at least one AE leading to early termination for all subjects ([Table 60](#) and [Table 61](#)).

Adverse events occurring in 5% of subjects (by MedDRA preferred term) in any treatment group will be presented ([Table 63](#)).

The proportion of subjects reporting at least one adverse event will be summarized by MedDRA system organ class and preferred term for each treatment arm, actual baseline ordinal score and overall. Denominators for percentages are the number of subjects in the Treated population.

The following summaries for adverse events will be presented by MedDRA system organ class, preferred term, baseline ordinal score and treatment group:

- Renal adverse events by preferred term ([Table 64](#));
- Hepatic adverse events by preferred term ([Table 65](#))
- Related adverse events by MedDRA system organ class and preferred term ([Table 66](#));
- Subject listing of non-serious adverse events ([Listing 13](#)) and listing of related adverse events ([Listing 14](#));
- Bar chart of non-serious related adverse events by actual baseline ordinal score and MedDRA system organ class ([Figure 25](#), [Figure 26](#));

A table of new diagnoses between the Day 29 visit and the Day 60 visit will be summarized by condition, treatment arm, actual baseline ordinal score and overall ([Table 67](#)). Conditions reported at the Day 60 visit will be listed ([Listing 30](#)).

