15.2.2. Glucose Grading

No change to the grading per the DAIDS Toxicity Table. However, a baseline condition of diabetes mellitus will be factored into reporting of grade 3 or grade 4 adverse events, as follows:

- If a subject has no history of any type of diabetes mellitus and baseline glucose levels are normal, grade 1 or grade 2, then any grade 3 or 4 glucose spike will be reported as an AE.
- If a subject has a history of any type of diabetes mellitus, then:
 - All grade 4 glucose elevations will be reported as AEs.
 - If baseline glucose levels are normal, grade 1, grade 2 and there are two or more consecutive elevations of glucose to grade 3, this will be reported as an AE.
 - If baseline glucose levels are normal, grade 1 or grade 2, a single elevation of glucose to grade 3 will not be reported as an AE or reported as related to Dexamethasone.

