	Day 5	Baricitinib + PBO + RDV	x	x	X	x	x	x	x		
		PBO + Dexamethasone + RDV	x	x	X	x	x	x	x		
	Day 8	Baricitinib + PBO + RDV	x	x	X	x	x	x	x		
		PBO + Dexamethasone + RDV	x	x	X	x	x	x	x		
	Day 11	Baricitinib + PBO + RDV	x	x	X	x	x	x	x		
		PBO + Dexamethasone + RDV	x	x	X	x	x	x	x		
	Day 15	Baricitinib + PBO + RDV	x	x	X	x	x	x	x		
		PBO + Dexamethasone + RDV	x	x	X	x	x	x	x		
	Day 29	Baricitinib + PBO + RDV	x	x	X	x	x	x	x		
		PBO + Dexamethasone + RDV	x	x	X	x	x	x	x		
	Maximum Severity Post Baseline		x	x	X	x	x	x	x		
			x	x	X	x	x	x	x		
Each parameter will be summarized individually similar to the above...											
The “Max Post Baseline” rows indicate the maximum severity experienced by each subject at any time point post baseline, including unscheduled assessments and assessments beyond Day 29.											
N = Number of subjects in the As Treated Population											

Programming Note: Vitamin D, D-dimer and CRP results are not included in this table. Include all lab parameters that are being graded in this table.

Table 89: Treatment-Emergent Laboratory Abnormalities - As Treated Population, Actual Baseline Ordinal Score of 5 or 6

Laboratory Parameter	Maximum Post Baseline Grade	Baricitinib + PBO + RDV (N=X)			PBO + Dexamethasone + RDV (N=X)		
		N	n	%	N	n	%
Any Parameter	1	x	x	x	x	x	x
	2	x	x	X	x	x	x
	3	x	x	X	x	x	x
	4	x	x	X	x	x	x
	Any Grade	x	x	X	x	x	x
Continue for all graded parameters							
N = number of subjects in the As Treated Population with any post-baseline data available for the specified Lab Parameter.							
n = number of subjects in the As Treated Population with treatment emergent abnormalities for the specified Lab Parameter.							
A treatment emergent laboratory abnormality is defined as a post-baseline abnormal value with a severity grade greater than at baseline.							

Table 90: Summary Statistics of Laboratory Results by Parameter, Study Visit Day, and Treatment Group – As Treated Population, Actual Baseline Ordinal Score 5 or 6

Laboratory Parameter	Study Visit Day	Treatment Group	Absolute					Change from Baseline				
			N	Mean	95% CI	Median	Min, Max	N	Mean	95% CI	Median	Min, Max
Parameter 1	Baseline	Baricitinib + PBO + RDV	x	xx.x	xx.x, xx.x	xx.x	xx.x, xx.x	---	---	---	---	---
		PBO + Dexamethasone + RDV	x	xx.x	xx.x, xx.x	xx.x	xx.x, xx.x	---	---	---	---	---
	Day 3	Baricitinib + PBO + RDV	x	xx.x	xx.x, xx.x	xx.x	xx.x, xx.x	x	xx.x	xx.x, xx.x	xx.x	xx.x, xx.x

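### For subjects given same-day dexamethasone before randomization, Table 89 can count a laboratory abnormality measured before any study product as treatment-emergent, contrary to Section 9.3

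*SAP*

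**What the plan says.** SAP Section 3.3.1 gives two safety baselines. In general, "the baseline value will be defined as the last value obtained prior to the first on-trial dose of any study product". An exception follows: "A small subset of subjects may receive dexamethasone as standard of care on the same day as but prior to randomization" and "then forgo the dexamethasone / placebo component of the Day 1 study product administration". In that case, "for these subjects, the value of baseline safety assessments will be defined as the last value obtained prior to the dexamethasone dose". The exception names no arm, and could not, because the dose comes before randomization. Section 4.2.1 limits pre-study dexamethasone ("max 1 dose per inclusion criteria").

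Three other places use a starting point for safety:

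- Section 9.3, adverse events: "treatment emergent events are adverse events or events increasing in severity anytime following the initiation of administration with any study product".
- Appendix 1, Table 89, laboratory results: "A treatment emergent laboratory abnormality is defined as a post-baseline abnormal value with a severity grade greater than at baseline". The maximum-severity rows of Table 88 likewise take every time point after baseline, including unscheduled ones.
- Section 15.2.2 makes the glucose reporting rule depend on the baseline grade. It has every grade 3 or 4 value reported as an adverse event under this condition: "If a subject has no history of any type of diabetes mellitus and baseline glucose levels are normal, grade 1 or grade 2".

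**The concern.** For most subjects the baseline immediately precedes study product, so post-baseline and after study product mean the same thing. For this subset they do not: the period after baseline opens before a dose that is not study treatment. Table 89 has no second condition tying the value to study product, so it inherits the earlier start.

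The comparison is baricitinib against a steroid, and glucose and white cells are both listed safety endpoints. A steroid-related abnormality seen before any study product, in a subject then assigned to baricitinib, would appear in the baricitinib column as treatment-emergent. Under Section 9.3 the same finding would not be a treatment-emergent adverse event unless it worsened after study product began. Two safety tables would then disagree about the same patient.

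**Working it through.** **1. The definitions side by side.** Take one such subject in this order: (a) laboratory value, normal; (b) standard-of-care dexamethasone; (c) laboratory value, grade 3; (d) first on-trial dose of any study product; (e) Day 3 value, normal.

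- Section 3.3.1, general rule: baseline is (c).
- Section 3.3.1, exception: baseline is (a).
- Table 89 with the exception: (c) is post-baseline with a higher grade, so it is treatment-emergent.
- Section 9.3: (c) precedes study product, so it is not treatment-emergent.
- Section 3.3.14 also starts the safety composite clock at the first dose of study treatment.

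Table 89 is therefore the one out of line.

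**2. When it arises.** A value must fall at (c). Section 4.3 schedules draws on Day 1 and then Day 3. A Day 1 draw may fall in that gap, but an effect first seen on Day 3 is post-baseline under either baseline.

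**3. Size.** The SAP gives no figure here, so there is none to reproduce. All inputs are assumptions:

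- f, share of subjects in the subset: 5% to 30%
- q, chance that the dose produces an abnormality seen before the first on-trial dose: 5% to 10%
- pB = 10% and pD = 25%, rates without the extra dose under baricitinib and dexamethasone

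Exception as written. The dose stands in for the first infusion in the dexamethasone arm, so that rate stays at pD:

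- baricitinib = pB + f·q·(1 − pB)
- difference = pD − pB − f·q·(1 − pB)

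General rule instead, with an abnormality present at baseline never counted again:

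- baricitinib = pB − f·q·pB; dexamethasone = pD − f·q
- difference = pD − pB − f·q·(1 − pB), the same expression

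| f, q | Rule | Baricitinib | Dexamethasone | Difference | Ratio |
|---|---|---|---|---|---|
| 5%, 5% | as written | 10.2% | 25.0% | 14.8 points | 2.45 |
| 5%, 5% | general | 10.0% | 24.8% | 14.8 points | 2.48 |
| 30%, 10% | as written | 12.7% | 25.0% | 12.3 points | 1.97 |
| 30%, 10% | general | 9.7% | 22.0% | 12.3 points | 2.27 |

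Without any pre-randomization dose the difference is 15.0 points and the ratio 2.50. At f = 5% the baricitinib rate rises by at most 0.05 × 0.10 × 0.90 = 0.45 points.

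**4. What dating the value would do.** Let r be the share of these abnormalities still present after the first on-trial dose. With the exception kept and the value required to postdate study product, the baricitinib rate is pB + f·q·r·(1 − pB). At f = 30% and q = 10% this is 10.0% for r = 0, 11.35% for r = 0.5 and 12.7% for r = 1. The requirement removes transients only.

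**The case against.** The strongest defence is that the exception is reasoned and treats both arms alike. In the dexamethasone arm the standard-of-care dose takes the place of the skipped Day 1 infusion, and a baseline taken after it could hide the first steroid effect. A later baseline could also weaken glucose reporting: a non-diabetic subject whose post-dexamethasone value is already grade 3 would no longer meet the baseline condition in Section 15.2.2. Both arguments stand, and they are reasons to keep the exception. Neither explains why a value that precedes all study product should be called treatment-emergent.

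A reader might infer that the moved baseline dilutes the comparison between arms. Adjusting the baricitinib arm alone, with a subset of 5% to 20% and a 10% to 20% chance of an abnormality, seems to shrink 15.0 points to 14.6 to 11.4 (0.15 − 0.9 × 0.005 = 0.1455; 0.15 − 0.9 × 0.04 = 0.114). The documents do not support attributing that loss to the rule. Under full masking the general rule gives the same differences, because the loss comes from dexamethasone exposure shared by both arms. Full masking is itself an assumption. If only a fraction m of abnormalities present at baseline is masked, the general rule gives 15 − 2.7m points at f = 30% and q = 10%, for example 13.65 at m = 0.5 against 12.3 as written. The SAP does not determine m.

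A reader might also infer that treatment-emergent adverse events in general are affected. They are not: Section 9.3 ties them to study product whatever the baseline.

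**Conclusion.** The inconsistency is real and minor. For this subset, laboratory treatment emergence can begin before study product, while adverse-event treatment emergence cannot. The effect is confined to graded laboratory results and, through the baseline grade, the glucose reporting rule. It needs a value between the dexamethasone dose and the first on-trial dose.

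The size is unknown because the SAP gives no number for the subset. On the assumed inputs the baricitinib rate rises by 0.2 to 2.7 points over 10%. The ratio is 2.45 to 1.97 as written, against 2.48 to 2.27 under the general rule. The upper end uses a 30% share, which sits poorly with a subset described as small.

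No planned laboratory table would reveal the effect. The same-day dexamethasone subgroup in Section 6.4 serves the primary and key secondary efficacy outcomes, and the safety splits by prior dexamethasone (Tables 85 and 86) cover infections only.

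**What to change.** 1. Keep the exception in Section 3.3.1. Deleting it trades one distortion for another.
2. In the Table 89 footnote, and for the post-baseline maximum in Table 88, require the abnormal value to be dated after the first on-trial dose of any study product, matching Section 9.3. The missing-time rule in Section 3.3.1 already treats a same-date value without a time as preceding study product, so such values would not count.
3. Show Tables 89 and 90 by same-day dexamethasone (yes/no). Abnormalities that persist past the first on-trial dose still count under step 2, and this split shows how much they contribute.
4. Add a sensitivity table for these outputs using the last value before the first on-trial dose as baseline for everyone. An arm-specific baseline would not be valid.

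The cost is one line in two table shells, one additional split and one sensitivity table. No new data are needed.
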